#### 4.2.1.1 Adverse events

Even not stated explicitly, all summaries described below will be based on AEs during treatment and follow-up.

An overall summary of subjects with at least 1 AE in the following categories will be presented as event rates per 100 subject years. This summary will also be presented for the additional supportive treatment groups placebo feeder + anifrolumab 300 mg LTE, and anifrolumab 150 mg feeder + anifrolumab 300 mg LTE. This summary will also be presented for the LTE Study only.

- Any AE
- Any AE with outcome = death
- Any SAE (including events with outcome = death)
- Any AE leading to discontinuation of investigational product
- Any AE related to investigational product
- Any AE of severe intensity
- Any AESI
  - Any AESI of non-opportunistic serious infections
  - Any AESI of opportunistic infections
  - Any AESI of anaphylaxis
  - Any AESI of malignancy
  - Any AESI of herpes zoster
  - Any AESI of tuberculosis
  - Any AESI of influenza
  - Any AESI of vasculitis (non SLE)
  - Any AESI of major acute cardiovascular events
- Any other significant AE

The overall summary above will be repeated for the sub-periods prior to the COVID-19 pandemic (events prior to 11-Mar-2020) and during the COVID-19 pandemic (events on or after the COVID-19 pandemic; only subjects remaining in the study on 11-Mar-2020 will be included). These summaries will be presented for the LTE study only. Alternative event rates and event rates will be computed. As sensitivity analysis the overall summary will be repeated including subjects excluded from analysis (see Section 4.1.1).

An overall summary of subjects with at least one COVID-19 related AE in the following categories will be presented as alternative event rates per 100 subject years. This summary will be presented for the LTE Study only. Only subjects remaining in the study on 11-Mar-2020 will be included.

- Any COVID-19 related AE

- Any COVID-19 related AE with outcome = death
- Any COVID-19 related SAE (including events with outcome = death)
- Any COVID-19 related AE leading to discontinuation of investigational product
- Any COVID-19 related AE related to investigational product
- Any COVID-19 related AE of severe intensity

The event rate per 100 subject years including 95% CIs will be summarised for the following categories. Summaries of AESIs will be presented by AESI category (non-opportunistic serious infections, opportunistic infections, anaphylaxis, malignancy, herpes zoster, tuberculosis, influenza, vasculitis [non SLE], and major acute cardiovascular events) and preferred term. Summaries for SAEs will be presented by MedDRA system organ class and preferred term.

- Any AESI
- Any AESI by time interval for the first onset of event – alternative event rates
- Any AE leading to discontinuation of IP by time interval for the first onset of event – alternative event rates (combined feeder & LTE study, by preferred term)
- Any AESI – alternative event rates
- Any SAE (including events with outcome = death) (during treatment and during follow-up separately. No event rate for during follow-up will be presented)
- Any SAE (including events with outcome = death) by time interval for the first onset of event – alternative event rates

The event rate per 100 subject years will be summarised by MedDRA system organ class and preferred term for the following AE categories.

- Any AE (during treatment and during follow-up separately. No event rate for during follow-up will be presented)
- Any AE by descending preferred term (during treatment, and during the LTE treatment)
- Any AE with outcome = death
- Any SAE by descending preferred term (including events with outcome = death) (during treatment, and during the LTE treatment)
- Any AE leading to discontinuation of investigational product
- Any AE by relationship to investigational product (yes, no) (multiple occurrences of an AE in 1 subjects will only be counted once as related if at least one AE is related and as not related if all occurrences are not related)
- Any AE by maximum intensity (mild, moderate, severe) (i.e., multiple occurrences of an AE in 1 subjects will only be counted once with the maximum intensity in this AE)
- Any other significant AE

The alternative event rate per 100 subject years will be summarised by MedDRA preferred term for the following AE categories.

- Any COVID-19 related AE (for the LTE Study only, only subjects remaining in the study on 11-Mar-2020 will be included)
- Any SAE prior to the COVID-19 pandemic (for the LTE Study only)
- Any SAE during the COVID-19 pandemic (for the LTE Study only, only subjects remaining in the study on 11-Mar-2020 will be included)

Cardiovascular outcome events as determined by the CV-EAC will be presented separately, summarising the number of AEs submitted for adjudication and the outcomes of the adjudication including MACE classification. Site reported cardiovascular AEs, cardiovascular SAEs, and their corresponding adjudicated outcomes will be listed.

The time to first onset of an AE in an AESI category will be presented separately for each AESI category as a Kaplan-Meier plot annotated with the number of subjects at risk every 6 months.

Furthermore, the alternative event rates per 100 subject years for the first onset of herpes zoster will be summarized for events overall and by time intervals). The following subcategories will also be considered in this summary: SAE (including events with outcome of death), AE leading to discontinuation, and AE by maximum intensity (mild, moderate, and severe). This summary will also be presented for the additional supportive treatment groups placebo feeder + anifrolumab 300 mg LTE, and anifrolumab 150 mg feeder + anifrolumab 300 mg LTE.

Furthermore, AESIs (by event type and preferred term), SAEs (during treatment and during follow-up separately, by system organ class and preferred term) during LTE will be summarised by LTE treatment group. Summaries of deaths, AESIs by time interval and SAEs by time interval will also be presented for the additional supportive treatment groups placebo feeder + anifrolumab 300 mg LTE, and anifrolumab 150 mg feeder + anifrolumab 300 mg LTE.

The event rate per 100 subject years and number and percentage of subjects with at least one anaphylaxis, hypersensitivity, and infusion-related reaction (investigator), respectively, will be summarised overall as well as for the following respective subcategories: SAE (including events with outcome of death), AE leading to discontinuation, and AE by maximum intensity (mild, moderate, and severe). Furthermore, these AE categories will be presented graphically over time as percentage of subjects with a respective AE at a respective visit according to the definition as given in Section 3.1.1. These summaries will also be presented for the additional supportive treatment groups placebo feeder + anifrolumab 300 mg LTE, and anifrolumab 150 mg feeder + anifrolumab 300 mg LTE.

Infections, opportunistic infections, and non-opportunistic infections will be summarised with the same subcategories as given above. This summary will also be presented for the additional

supportive treatment groups placebo feeder + anifrolumab 300 mg LTE, and anifrolumab 150 mg feeder + anifrolumab 300 mg LTE.

Key subject information for subjects with an AE with outcome of death, subjects with serious AEs, subjects with an AE leading to discontinuation of investigational product, subjects with AESIs, subjects with a cardiovascular event, and subjects with a COVID-19 related AE, respectively, will be provided.

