### **1.3 Benefit/risk and ethical assessment**

A detailed assessment of the data supporting the overall risk/benefit of anifrolumab is discussed in the Investigator's Brochure (IB).

There is a significant unmet medical need for the treatment of subjects with chronic, moderately to severely active SLE. Since type I IFNs have a role in SLE, a therapy that targets type I IFN receptors, such as anifrolumab, may be beneficial in the treatment of these subjects.

Anifrolumab demonstrated a clinically relevant benefit in subjects with moderate to severe SLE treated with standard of care (SOC). The efficacy was supported by a broad range of clinical measures of global (various levels of SLE Responder Index responses, British Isles

Lupus Assessment Group-based Composite Lupus Assessment) and organ-specific disease activity (Cutaneous Lupus Erythematosus Disease Area and Severity Index, joint count). A clinically relevant increase in the proportion of subjects achieving pre-specified corticosteroid reduction in the 300 mg group was also observed compared with placebo.

In this study, anifrolumab will be administered at a fixed IV dose of 300 mg Q4W for 156 weeks (the last dose of investigational product will be given at Week 152), equivalent to the lower dose in the Phase 2 study (CD-IA-MEDI-546-1013).

Anifrolumab was generally well tolerated. A dose-related increase in the reporting rate of herpes zoster reactivation with cutaneous presentation was observed in patients receiving anifrolumab compared with placebo. Herpes zoster reactivation with cutaneous presentation is an identified risk for anifrolumab. No other infectious risks have been identified; however, this continues to be closely monitored. Although anifrolumab is a human mAb, patients can develop anti-drug antibodies (ADAs) that may neutralize the activity of the drug or may be associated with acute or delayed hypersensitivity reactions, including anaphylaxis. Furthermore, the administration of any foreign protein may be associated with acute allergic or hypersensitivity reactions that may be severe and may result in death. Patients will be monitored for the presence of and the clinical manifestations associated with the formation of specific antibodies to anifrolumab.

As of 18 January 2017, a total of 2 severe hypersensitivity events have occurred in clinical studies of anifrolumab, although these events remain blinded. Careful monitoring for such events will continue.

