In addition to the ongoing, blinded review provided by the PRA Medical Monitor, an independent Data and Safety Monitoring Board (DSMB) reviews safety data on a regular basis throughout the study (see Section 6.10.1).

AstraZeneca considers that the available non-clinical and clinical data indicate an acceptable safety profile for anifrolumab. Protocol-defined exclusions are in place to prevent enrolment of patients with infection and malignancy risks that might compromise their safety. AESIs, such as herpes zoster reactivation with cutaneous presentation, as well as other herpes zoster-associated adverse events (AEs), anaphylaxis, opportunistic infections, serious infections, influenza, TB (including latent TB), malignancies, major adverse cardiovascular events (MACE), and vasculitis (non-SLE), are being closely monitored in clinical studies.

The proposed dosing regimens for the Phase 3 studies are supported by positive Phase 2 efficacy data and an acceptable safety profile. The management plan for identified, potential, and important potential risks associated with anifrolumab is designed to minimize risk to patients, and the emerging safety profile supports continued investigations. AstraZeneca considers that anifrolumab continues to demonstrate an overall positive benefit risk balance to support its further clinical evaluation.

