### **6.5 Adverse events of special interest**

An AESI is an AE of scientific and medical concern specific to understanding biologics and requires close monitoring and rapid communication by the Investigator to the Sponsor/Sponsor's delegate. An AESI may be serious or nonserious.

Adverse events of special interest in this protocol will be assessed at each visit on the CRF. The events of interest are medically significant infections (non-opportunistic serious infections and opportunistic infections including viral infection/reactivation), severe hypersensitivity reactions including anaphylaxis and immune complex disease, malignancy, *herpes zoster* with cutaneous presentation, TB (including latent TB), influenza, vasculitis (non SLE), and MACE (including stroke, myocardial infarction, or cardiovascular death). Lupus nephritis (associated with SLE; WHO or ISN/RPS Classification Class III, IV or V) is defined

not as an AESI but as a new SLEDAI AE, and diagnosis will be supported with laboratory results.

An AESI that meets 1 of the seriousness outcomes listed in Section 6.2 will be categorised as an SAE for the purposes of follow-up responsibility and safety reporting. A nonserious AESI will be categorised as an AE. For reporting of AESIs, see Section 6.8.

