#### **6.5.2 Severe hypersensitivity reactions including anaphylaxis and immune complex disease**

Anaphylaxis is a severe, potentially fatal, systemic allergic reaction that occurs suddenly after contact with an allergy-causing substance, such as investigational product. For the purposes of this study, the definition [REDACTED] is provided as a simple and rapid means to make the diagnosis of anaphylaxis during infusion with investigational product. This definition was a product of a symposium convened by the National Institute of Allergy and Infectious Diseases and Food Allergy and Anaphylaxis Network ([Sampson et al, 2006](#)).

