## 6.9 Management of investigational product-related toxicities

### 6.9.1 Anaphylaxis, hypersensitivity, and infusion-related reactions

Infusion-related reactions have been reported with the administration of IV Ig and mAb. As with any antibody, allergic reactions to dose administration are possible. Therefore, appropriate drugs and medical equipment to treat acute anaphylactic reactions must be immediately available, and study personnel must be trained to recognise and treat anaphylaxis. For a definition of anaphylaxis, hypersensitivity reactions, and infusion-related reactions, [REDACTED]

Subjects should not be premedicated unless they have had a prior infusion-related reaction to anifrolumab. However, if a prior infusion-related reaction has been documented, the Investigator may elect to administer prophylactically an antihistamine and/or acetaminophen/paracetamol for the comfort and safety of the subject prior to subsequent infusions. Prophylactic use of glucocorticosteroids prior to subsequent infusions is not permitted.

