## 8.4 Outcome measures for analyses

### 8.4.1 Primary outcome variables: Safety variables

The following primary safety data will be collected: AESIs (see Section 6.5) and SAEs.

Other safety variables include AEs, vital signs, physical examination, ECGs, flares as defined by a modification of the SELENA Flare Index using the SLEDAI-2K, haematology, clinical chemistry, and urinalysis.

Adverse events, AESIs, and SAEs will be summarised by means of descriptive statistics and qualitative summaries.

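### The SAP's AESI categories name only anaphylaxis where the protocol defines a wider severe hypersensitivity class, and the separate hypersensitivity row is tied to one preferred term and one lower level term

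*SAP*

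**What the plan says.** **Protocol.** Section 8.4.1 sets the primary outcome: "The following primary safety data will be collected: AESIs (see Section 6.5) and SAEs". Section 6.5 includes among the AESIs "severe hypersensitivity reactions including anaphylaxis and immune complex disease", and section 6.5.2 carries the same title, "Severe hypersensitivity reactions including anaphylaxis and immune complex disease". The visible text of 6.5.2 describes anaphylaxis only; part of that section is redacted.

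**SAP, AESI categories.** Section 4.2.1.1 lists the AESI categories twice, once for the overall summary and once for the rate tables. Both lists have nine entries, and the only allergic entry is anaphylaxis. The rate tables are presented "by AESI category (non-opportunistic serious infections, opportunistic infections, anaphylaxis, malignancy, herpes zoster, tuberculosis, influenza, vasculitis [non SLE], and major acute cardiovascular events)" and by preferred term. The same categories drive the time-interval rates and the Kaplan-Meier plots of time to first onset. Section 3.1.1 says that AESIs are identified by a mark in the eCRF. It does not say which eCRF category or terms fill the anaphylaxis row. The visible SAP does not mention immune complex disease.

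**SAP, hypersensitivity.** Section 4.2.1.1 also has a summary and a by-visit graph for three adverse event groups: anaphylaxis, hypersensitivity and infusion-related reaction. This sits outside the AESI category lists. Section 3.1.1 defines hypersensitivity as preferred term *Hypersensitivity* and lower level term *Hypersensitivity reaction*, joined by *and*.

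**The concern.** AESI rates are the primary outcome, and the SAP reports them by category. Protocol 1.3 explains why this class matters: anti-drug antibodies "may be associated with acute or delayed hypersensitivity reactions, including anaphylaxis". It also counts past cases under the wider heading, stating that "a total of 2 severe hypersensitivity events have occurred in clinical studies of anifrolumab".

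If the SAP row is as narrow as its name, the report gives no category rate and no time to first onset for the class the protocol defines. The gap matters most for a severe reaction that is not serious. Protocol 6.5 allows a nonserious AESI and 6.6.3 separates severity from seriousness, so such an event would not be picked up in the SAE rates either.

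The two-term rule is a separate matter. It sets what the hypersensitivity row and its by-visit graph can contain, and read literally it is narrow.

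**Working it through.** **Step 1: line up the categories.** With medically significant infections split into serious non-opportunistic and opportunistic, Protocol 6.5 gives nine AESI types. The SAP also has nine. Eight correspond, some under shortened names. The ninth is the severe hypersensitivity class in the protocol and anaphylaxis in the SAP.

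**Step 2: does the SAP use anaphylaxis to mean the whole class?** In SAP 3.1.1 (the by-timepoint rule) and in the 4.2.1.1 summary, anaphylaxis, hypersensitivity and infusion-related reaction are three separate groups. Protocol 6.9.1 separates them too: "For a definition of anaphylaxis, hypersensitivity reactions, and infusion-related reactions". If anaphylaxis meant the whole class in the AESI lists, the SAP would be using one word in two senses without saying so.

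**Step 3: where would a flagged, non-anaphylactic severe reaction be counted, on the literal reading?**

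| Output | Counted? |
|---|---|
| Any AESI, overall and by time interval | Yes |
| All-AE tables by preferred term | Yes |
| Key subject information for AESIs | Yes |
| SAE tables, including time-interval rates | Only if serious |
| AESI category rate with 95% CI | No |
| AESI category rate by time interval | No |
| AESI category Kaplan-Meier plot | No |
| Hypersensitivity row and by-visit graph | Only if both terms apply |

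**Step 4: the two-term rule.** Two kinds of event fall outside the hypersensitivity row: the same preferred term reached through another lower level term, and an allergic event under another preferred term. Those counted as anaphylaxis or infusion-related reaction still appear in the same summary and graph, in their own rows.

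**Step 5: illustration of size.** The documents give no count for this trial. SAP 4.1.3 names exact Poisson limits. (The formula printed there uses the log of the rate and cannot be evaluated at zero events, so I use the exact limits.) With x events in T subject-years:

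- lower = χ²(0.025; 2x) / 2 / T, taken as 0 when x = 0
- upper = χ²(0.975; 2x + 2) / 2 / T

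*Check against the plan's own figure.* At 10 per 1000 over 893 subject-years, x = 8.93. The limits are 4.56 to 19.03 per 1000, as printed in SAP 4.1.3.

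*Inputs.* T = 893 (Randomised Anifrolumab 300 mg) and T = 1343 (All Anifrolumab, which SAP 4.2.1 uses for rare events), both from SAP 1.3. x = 2 is borrowed from the two severe hypersensitivity events in Protocol 1.3. I assume that each is a different subject, that both fall in the group shown, and that neither counts as anaphylaxis.

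*Results per 100 subject-years.* For x = 0 the upper numerator is 3.689. For x = 2 the numerators are 0.242 and 7.225.

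| Group | Anaphylaxis row, x = 0 | Protocol class, x = 2 |
|---|---|---|
| T = 893 | 0 (0 to 3.689/8.93 = 0.41) | 2/8.93 = 0.22 (0.03 to 0.81) |
| T = 1343 | 0 (0 to 3.689/13.43 = 0.27) | 2/13.43 = 0.15 (0.02 to 0.54) |

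**The case against.** The best defence of part one is that anaphylaxis is a short label for the whole class. Other SAP names are shortened: tuberculosis stands for TB including latent TB, and nobody would conclude that latent TB was dropped. Nine types face nine categories, so anaphylaxis fills the remaining slot. Protocol 1.3 uses the same short form when it lists AESIs: "anaphylaxis, opportunistic infections, serious infections, influenza, TB (including latent TB". The eCRF and the table shells, which SAP 4.1.3 places in a separate document, are not available. Parts of Protocol 6.5.2 and 6.9.1 and of SAP section 6 are redacted. If the row does hold the class, its preferred terms are already shown beneath it.

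This stands as a real possibility, and it makes part one conditional. It does not settle the matter. The Protocol 1.3 list is given as examples, while Protocol 8.4.1 points to section 6.5. The SAP itself treats anaphylaxis and hypersensitivity as separate, and the visible text of SAP 3.1.1 does not say what fills the row.

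On part two, the defence is that the rule is explicit and reproducible, that no AESI category depends on it, and that the visible protocol asks for no such grouping. *And* may also have been meant as *or*. All of this limits the weight of the point, but as written the rule still excludes events that share the preferred term.

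A reader might infer that all other allergic events are missing from the summary and graph. That goes too far: events counted as anaphylaxis or infusion-related reaction are in both. Only the hypersensitivity row is narrow.

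**Conclusion.** Both parts hold, within limits.

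1. On a literal reading, flagged severe non-anaphylactic reactions and immune complex disease events have no AESI category rate with confidence interval, no category time-interval rate and no Kaplan-Meier curve. If anaphylaxis is only a short label, the defect is the label.
2. The hypersensitivity row and its by-visit graph leave out events with the same preferred term under another lower level term. They also leave out allergic events under other preferred terms that are not counted as anaphylaxis or infusion-related reaction.

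The number of affected events is unknown. The intervals above rest on assumed placement of two events that came from anifrolumab studies in general, were blinded, and are not described by type. If both were anaphylaxis, the effect in the example is nil.

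Two stronger conclusions are tempting. One is that events are lost from the primary outcome. The documents do not support this, since flagged events remain in the any-AESI total and all remain in the adverse event tables. The other is that the SAP deliberately narrowed the protocol class. The visible part of SAP section 6 records no such change, part of that section is redacted, and the eCRF is not available. No formal comparison is planned, so no test result changes.

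The changes are worth making because they are specific, cheap and can alter reported safety rates. Confidence is medium, because part one depends on material not supplied.

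**What to change.** **AESI category.** In SAP 4.2.1.1, use the protocol's severe hypersensitivity class as the category row in the rate tables, time-interval tables and Kaplan-Meier plots. Show anaphylaxis beneath it, and immune complex disease as a further sub-row if wanted. State in SAP 3.1.1 which eCRF category or terms fill the row. If the eCRF category already holds the whole class, relabel the row and say so.

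**Hypersensitivity definition.** In SAP 3.1.1, drop the lower level term condition and define hypersensitivity by a list of preferred terms fixed before database lock. If lock has already passed, give the mapping and the list as a dated late clarification.

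**Cost.** SAP wording, one medical review of the term list and minor table reprogramming. No new data are needed, since only recorded events are re-categorised.
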